The Office of Rare Diseases (ORD) of the National Institutes of Health (NIH) established a Rare Diseases Clinical Research Network (RDCRN) in collaboration with other NIH Institutes and has funded several rare diseases clinical research consortia and one Data Management and Coordinating Center. The Porphyrias Consortium was created as part of the RDCRN, to study the human porphyrias. The Porphyrias Consortium is a consortium of the academic institutions listed in the participating institutions table. All Centers in the Porphyrias Consortium are participating in this study. Additional centers may be added if funding is available.

2. Specific Aims (Hypothesis and Objectives)

The overall objectives of this study are to determine the efficacy and safety of oral iron administration in the protoporphyrrias. Efficacy will be based on erythrocyte protoporphyrin levels, photosensitivity, other clinical symptoms, and quality of life in patients with EPP and XLP who have diminished iron stores (serum ferritin ≤ 30 ng/ml).

Primary Objective: To determine if oral iron therapy can decrease erythrocyte protoporphyrin levels in patients with EPP and XLP.

Secondary Objectives:

- 1) To assess whether oral iron therapy can improve iron status and decrease plasma porphyrin levels and clinical symptoms
- 2) To assess if there is an improvement in the quality of life in treated patients

This is an open label pilot study of the safety and efficacy of oral iron therapy in patients with EPP and XLP with diminished iron stores as defined by serum ferritin level.

3. Background

Erythropoietic Protoporphyrinia (EPP) is characterized by painful, non-blistering, cutaneous photosensitivity, with onset in early childhood. EPP is the most common porphyria in children and the third most common in adults (after porphyria cutanea tarda and acute intermittent porphyria). Reports of prevalence vary between 5 and 15 cases per million population. (2-4)

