4.5 Data Elements

The following laboratory tests and procedures will be used as the primary data elements:

- Erythrocyte protoporphyrin
- Plasma total porphyrins
- A complete blood count with differential
- Iron studies (serum iron, TIBC, Transferrin saturation)

- Serum ferritin
- Hepatic function panel (serum ALT, AST, alkaline phosphatase, total and direct bilirubin, albumin, total protein)
- EPP-specific Quality of Life Questionnaire

These will be completed at each study visit, and an adverse event review will be completed bi-weekly.

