4.6 Study Procedures

Baseline/Screening Visit:

- Patients will be admitted to the Clinical Research Unit or a comparable facility for ~2 hours. All patients will be enrolled in the Longitudinal Study and the diagnosis of EPP or XLP and inclusion/exclusion criteria will be reviewed prior to baseline visit.
- A complete history and physical exam will be performed
- All concomitant medications will be recorded- if the subject is currently taking an iron supplement they will be instructed to discontinue it for at least 4 weeks and return for re-screening.
- Subjects taking Lumitene at screening will be asked to discontinue it for at least 4 weeks and return for re-screening.
- Patients will be asked to complete an EPP-specific quality of life questionnaire
- Laboratory studies will include:
 - A complete blood count with differential
 - Serum iron
 - TIBC
 - Serum ferritin
 - Transferrin saturation
 - Hepatic function panel
 - Erythrocyte protoporphyrin levels with metal-free and zinc ratio
 - Plasma total porphyrins
- Two yellow top ACD tubes will be collected and banked for future RNA and protein studies in this patient population
- Subjects will be instructed to take ferrous sulfate 325 mg BID with water starting the next day on an empty stomach following discharge.
Subjects will be discharged with a 3 month supply of medication with some surplus to account for dropped pills.

The first dose of oral ferrous sulfate (two 325 mg tablets) will be administered within 30 days of the screening visit.

For patients with a borderline ferritin level, re-screening will be allowed within 60 days of the original screening date. Only ferritin and erythrocyte protoporphyrin levels should be done at the re-screening visit. If the ferritin level is ≤ 30 ng/mL on re-screening, the first dose of oral ferrous sulfate will be administered within 30 days of the re-screening visit.

Follow Up Phone Calls:

- Coordinators will call the subject once a month (+/- 7 days) to review adverse events and concomitant medications.

3 Month, 6 Month, and 9 Month Study Visits (+/- 7 days):

- A review of systems will be performed, a physical exam will only be performed at the 6 Month visit
- Adverse events will be reviewed
- All concomitant medication changes will be recorded
- Patients will be asked to complete an EPP-specific quality of life questionnaire
- Laboratory studies will include:
 - A complete blood count with differential
 - Serum iron
 - TIBC
 - Serum ferritin

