4.7 Schedule of Events

	Screening	Day 0	1 Month 2 Month (via telephone)	3 Month	4 Month 5 Month (via telephone)	6 Month	7 Month 8 Month (via telephone)	9 Month	10 Month 11 Month (via telephone)	12 Month
	(Day -30 to -1)		(± 7 Days)	(± 7 Days)	(± 7 Days)	(± 7 Days)	(± 7 Days)	(± 7 Days)	(± 7 Days)	(± 7 Days)
Informed Consent	X									
Inclusion/Exclusion Criteria Review	X									
Labs (CBC, Iron, TIBC, Ferritin, Transferrin Sat, HFP)	X			X		X		X		X
Erythrocyte protoporphyrin levels & plasma porphyrins	X			X		X		X		X
2 Yellow top ACD tubes for banked samples	X					X				X
Urine/serum Pregnancy	X					X				X
Medical History review	X									
Review of Systems	X					X				X
Physical Exam	X					X				X
Vital Signs	X			X		X		X		X
EPP QoL Questionnaire	X			X		X		X		X
Provide 3 Month Supply of Medication		X*		X		X		X		
Pill Count				X		X		X		X
Con Med Review	X			X		X		X		X
AE Review			X	X	X	X	X	X	X	X
Review Compliance			X		X		X		X	

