Safety Endpoints: The primary safety endpoints will be an increase in reported clinical symptoms or a 35% increase in erythrocyte protoporphyrin levels. If an increase of 35% over baseline erythrocyte protoporphyrin levels is observed this test will be repeated after 2-4 weeks without discontinuing iron. If the level remains elevated $\geq 35\%$ on repeat testing then the study drug will be discontinued. If clinical symptoms increase to the point where the patient or treating physician is not comfortable continuing then the study drug should be discontinued. The secondary safety endpoints will be any increase in plasma porphyrins and side effects of oral iron therapy such as GI irritation, constipation, diarrhea, nausea, vomiting, and dark stools. If these secondary safety endpoints occur then discontinuing the oral iron will be at the discretion of the treating physician.

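### Re-screening for borderline ferritin repeats only two tests, so the other safety and secondary-outcome baselines can be 90 days old at first dose instead of 30

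*Combined protocol and SAP*

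**What the plan says.** Section 4.6 has two timing rules. On the standard path the first dose "will be administered within 30 days of the screening visit". For borderline ferritin, "re-screening will be allowed within 60 days of the original screening date", and if ferritin then qualifies, "the first dose of oral ferrous sulfate will be administered within 30 days of the re-screening visit". The content of that second visit is restricted: "Only ferritin and erythrocyte protoporphyrin levels should be done at the re-screening visit".

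Section 4.7 puts the CBC, iron studies, hepatic panel, plasma porphyrins, quality-of-life questionnaire and the row "Urine/serum Pregnancy" in the Screening column, headed Day -30 to -1. None of these is marked at Day 0, and there is no re-screening column. The pregnancy test does not appear in the laboratory list of 4.6. After screening it is next marked at month 6.

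Section 4.5 lists seven data elements and says: "These will be completed at each study visit". Re-screening repeats two of the seven.

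**The concern.** The restriction is an instruction, not a gap: a site that follows 4.6 to the letter does not repeat the other tests. If dosing then falls more than 30 days after the original screening, those tests lie outside the window in 4.7. A site that keeps the 4.7 window has to depart from 4.6.

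The items left out have uses in the plan:

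- Pregnancy and clinically significant liver dysfunction are exclusions (section 4.2), so the age of the tests behind them matters when iron is started.
- A rise in plasma porphyrins is a secondary safety endpoint (section 5.3), which needs a pre-dose reference value.
- The first secondary objective in section 2 is "To assess whether oral iron therapy can improve iron status and decrease plasma porphyrin levels and clinical symptoms", and the second concerns quality of life. For re-screened patients the before-after description of these measures would start up to 60 days earlier than for the rest.
- The iron baseline is split. The qualifying ferritin comes from re-screening, while serum iron, TIBC and transferrin saturation come from an earlier draw, when ferritin was borderline (read here as just above 30 ng/mL; the protocol does not define the term).

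**Working it through.** Inputs, all from sections 4.6 and 4.7:

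- screening to first dose, standard path: at most 30 days
- original screening to re-screening, borderline ferritin: at most 60 days
- re-screening to first dose: at most 30 days
- screening window in the schedule: Day -30 to Day -1

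**Standard path.** Maximum age of a screening value at first dose = 0 - (-30) = 30 days. Sections 4.6 and 4.7 agree.

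**Re-screening path, tests repeated** (ferritin, erythrocyte protoporphyrin). Maximum age = 30 days, as on the standard path.

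**Re-screening path, tests not repeated.** Maximum age = 60 + 30 = 90 days. The excess over the standard path is 90 - 30 = 60 days, and the ratio is 90/30 = 3.

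**Split iron baseline.** The largest gap between the qualifying ferritin and the serum iron, TIBC and transferrin saturation values is the screening-to-re-screening window, 60 days.

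**Data elements in 4.5.** Seven are listed: erythrocyte protoporphyrin, plasma porphyrins, CBC, iron studies, ferritin, hepatic panel and quality of life. Two are repeated, so 7 - 2 = 5 are not.

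**Pregnancy test.** This is the least certain item. If the restriction covers everything done at re-screening, the limit is 90 days. If it only trims the laboratory list in 4.6, the 4.7 window still governs the pregnancy test and the limit is 30 days. The text does not settle which.

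**After an unconditional repeat at re-screening.** Maximum age of every repeated item = 30 days.

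**Why a conditional repeat would not be enough.** Suppose the other tests were repeated only when dosing is expected more than 30 days after the original screening. A patient re-screened on day 10 with dosing planned for day 28 would not have them repeated. If dosing slips to day 40, it is still within the rule (40 - 10 = 30 days after re-screening), but the tests are 40 days old.

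**The case against.** The restriction may be deliberate, to spare patients and budget. It re-measures the two things that matter most: the eligibility criterion in doubt and the primary outcome. The other values are still pre-treatment. Section 6 analyses quality of life only descriptively and sets out no baseline-referenced analysis of iron studies or plasma porphyrins beyond descriptive laboratory findings. The documents list no fetal risk of the drug, and the schedule already accepts about six months between pregnancy tests on treatment. Section 7.1 has the site attest eligibility at registration, although it requires no test. These points stand, and they keep the matter small. They do not remove the conflict between 4.6 and 4.7.

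Three stronger readings are tempting, and the documents do not support them.

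- A reader might infer bias in the primary outcome. Erythrocyte protoporphyrin is repeated at re-screening, so a value no more than 30 days old is available for every patient.
- A reader might infer that the 35% discontinuation rule is undermined, because re-screened patients have two pre-treatment protoporphyrin values and neither section 6 nor 5.3 names the baseline. That is a separate missing definition, which the restriction does not cause. Its effect would depend on a gap between the two values that the documents do not give. Section 3 reports little within-person variation, and 5.3 stops the drug only if the rise persists on a repeat test.
- A reader might infer that women will certainly be dosed on a 90-day-old pregnancy test. The window in 4.7 has no stated exception, so a site could properly repeat that test.

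**Conclusion.** The point holds as a minor inconsistency with a cheap remedy. Five of the seven data elements can be up to 90 days old at first dose, against 30 on the standard path and in the schedule. The pregnancy test can be too, if the restriction is read to cover it.

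This rests on three things. First, 90 days is a maximum, reached only when both windows are fully used. Second, 4.6 is taken as an exception to the window in 4.7; if 4.7 governs, the two sections contradict each other and sites need to be told which to follow. Third, no Day 0 check exists in text we cannot see: the footnote to the Day 0 mark and the text just before section 4.1 are not in the copy reviewed. The mark sits on the medication-supply row, so a clinical check there is unlikely but possible.

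The number of patients affected is unknown and could be zero. Patients re-screened after stopping iron or Lumitene fall under a different sentence of 4.6 and are outside this point. It is worth considering, with moderate confidence.

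**What to change.** Replace the restricting sentence in 4.6 with an unconditional rule:

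> At re-screening, repeat ferritin, erythrocyte protoporphyrin, plasma porphyrins, CBC, serum iron, TIBC, transferrin saturation, the hepatic panel, the QoL questionnaire and, for women of childbearing potential, the pregnancy test; these re-screening values serve as baseline.

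Because the first dose must follow within 30 days, all of these are then at most 30 days old and fit the screening window in 4.7. The iron studies and the qualifying ferritin come from the same visit, and the last clause also settles which protoporphyrin value is baseline for re-screened patients.

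The cost is one sentence in the protocol and, per re-screened patient, a slightly larger draw at a visit that already takes blood, one questionnaire and, for women of childbearing potential, one pregnancy test. Nothing changes for patients who are not re-screened.

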4.7 Schedule of Events

	Screening	Day 0	1 Month 2 Month (via telephone)	3 Month	4 Month 5 Month (via telephone)	6 Month	7 Month 8 Month (via telephone)	9 Month	10 Month 11 Month (via telephone)	12 Month
	(Day -30 to -1)		(± 7 Days)	(± 7 Days)	(± 7 Days)	(± 7 Days)	(± 7 Days)	(± 7 Days)	(± 7 Days)	(± 7 Days)
Informed Consent	X									
Inclusion/Exclusion Criteria Review	X									
Labs (CBC, Iron, TIBC, Ferritin, Transferrin Sat, HFP)	X			X		X		X		X
Erythrocyte protoporphyrin levels & plasma porphyrins	X			X		X		X		X
2 Yellow top ACD tubes for banked samples	X					X				X
Urine/serum Pregnancy	X					X				X
Medical History review	X									
Review of Systems	X					X				X
Physical Exam	X					X				X
Vital Signs	X			X		X		X		X
EPP QoL Questionnaire	X			X		X		X		X
Provide 3 Month Supply of Medication		X*		X		X		X		
Pill Count				X		X		X		X
Con Med Review	X			X		X		X		X
AE Review			X	X	X	X	X	X	X	X
Review Compliance			X		X		X		X	

4.8 Investigational Product

All study drug will be stored and dispensed from individual centers' research pharmacies. All study drug will be provided to each site Par Pharmaceuticals directly.

Obtaining Study Drug: Each site is provided with an initial years' supply of study drug for five patients.

Dispensing, Dosage, and Accountability: All participants will receive treatment for a total of one year. Study drug will be dispensed with 3 month supplies. It is recommended that 2 weeks of additional drug is provided with each 3 month supply.

The dosage is 325 mg taken twice daily for a total of 650 mg daily. Tablets should not be broken or chewed.

At each study visit the participant will bring all study drug with them. The site coordinator will count and reconcile all study medication at each visit. At each visit (3, 6, 9 and 12 months) the subject will return all previous study drug and empty bottles and receive a new 3 month supply. At the final visit (12 months) a new supply will not be issued.

Study Drug Destruction: After proper documentation, medication returned by subjects can be destroyed onsite per institutional SOP.

If sites require additional study drug contact the PC Project Manager at least 2 months before it is needed on site.

5.0 Data and Safety Monitoring Plan

The study protocol will be reviewed and approved by the National Institutes of Health (NIH) and the Data Safety Monitoring Board (DSMB) before submission to individual center IRBs for approval. Participant enrollment may only begin with IRB approved consent forms.

This is an interventional pilot study that meets the federal definition of moderate risk.

5.1 Study Oversight

The Study Chair has primary oversight responsibility of this clinical trial. The NIH appointed Data Safety Monitoring Board (DSMB) has oversight responsibility of the Data Safety Monitoring Plan (DSMP) for this clinical trial. The DSMB will review accrual, patterns and frequencies of all adverse events, and protocol compliance every 6 months. The DSMB makes recommendations to the NIH regarding the continuation status of the protocol.

Each site's Principal Investigator and their research team (co-Investigators, research nurses, clinical trial coordinators, and data managers) are responsible for identifying adverse events. Aggregate report- detailed by severity, attribution (expected or unexpected), and relationship to the study drug/study procedures – will be available from the DMCC for site review. Adverse events will be reviewed at each study visit by

the research team. A separate report detailing protocol compliance will also be available from the DMCC for site review on a monthly basis. The research team will then evaluate whether the protocol or informed consent document requires revision based on the reports.

5.2 Definitions and Standards

The Rare Diseases Clinical Research Network defines an adverse event as: "...an unfavorable and unintended sign, symptom or disease associated with a participant's participation in a Rare Diseases Clinical Research Network study."

Serious adverse events include those events that: "result in death; are life-threatening; require inpatient hospitalization or prolongation of existing hospitalization; create persistent or significant disability/incapacity, or a congenital anomaly/birth defects."

An unexpected adverse event is defined as any adverse experience...the specificity or severity of which is not consistent with the risks of information described in the protocol.

Expected adverse events are those that are identified in the research protocol as having been previously associated with or having the potential to arise as a consequence of participation in the study

All reported adverse events will be classified by the site investigator where the AE occurred using the current version of the Common Terminology Criteria for Adverse Events (CTCAE) developed and maintained by CTEP at National Cancer Institute.

As this study is considered an interventional trial, all adverse events, including those not directly related to study participation, will be reported as specified above.

5.3 Expected/Known Risks/Discomforts/Adverse Events Associated with Study Intervention and Procedures: Definition of Expected Adverse Events

Study Drug/Intervention:

Drug Information for Ferrous sulfate USP

Dosing: Adults- 325 mg capsule administered twice daily (total 650 mg daily)

Human Toxicity/ Adverse Events (adapted from http://www.drugs.com/ferrous_sulfate.html): GI irritation, constipation, diarrhea, nausea, vomiting, and dark stools. In addition, as the effects of oral iron are unknown, patients may develop an increase in erythrocyte or plasma protoporphyrin levels and worsening clinical symptoms.

Study Procedures:

Physical Exam: A complete physical will be conducted every 6 months

Venipuncture: The vein in which the needle has been inserted to draw blood may become sore and red. A temporary bruise may develop, and rarely fainting may occur. The amount of blood, 24mL (~2 tablespoons) required for the tests described in this study is within the guidelines for blood collection for patients with porphyria.

Urine Collection: A sample of urine will be collected. This procedure does not expose the patient to any risk.

Safety Endpoints: The primary safety endpoints will be an increase in reported clinical symptoms or a 35% increase in erythrocyte protoporphyrin levels. If an increase of 35% over baseline erythrocyte protoporphyrin levels is observed this test will be repeated after 2-4 weeks without discontinuing iron. If the level remains elevated $\geq 35\%$ on repeat testing then the study drug will be discontinued. If clinical symptoms increase to the point where the patient or treating physician is not comfortable continuing then the study drug should be discontinued. The secondary safety endpoints will be any increase in plasma porphyrins and side effects of oral iron therapy such as GI irritation, constipation, diarrhea, nausea, vomiting, and dark stools. If these secondary safety endpoints occur then discontinuing the oral iron will be at the discretion of the treating physician.

5.4 Reporting Timeline

- Within **24 hours** (of learning of the event), investigators must report any reportable Serious Adverse Event (SAE) that:
 - Is considered life-threatening/disabling or results in death of subject
 - OR-
 - Is Unexpected/Unanticipated
- Investigators must report all other reportable SAEs within **5 working days** (of learning of the event).
- All other (suspected) reportable AEs must be reported to the RDCRN within **20 working days** of the notification of the event or of the site becoming aware of the event.

Local institutional reporting requirements to IRBs, any GCRC oversight committee and the FDA, if appropriate, remain the responsibility of the treating physician and the Study Chair.

5.5 RDCRN Adverse Event Data Management System (AEDAMS)

Upon entry of a serious adverse event, the DMCC created Adverse Event Data Management System (AEDAMS) will immediately notify the Study Chair, site PIs, the Medical Review Officer, and any additional agencies (if applicable- industry sponsor,) of any reported adverse events via email.

Serious adverse events: The NIH appointed Medical Review Officer (MRO) reviews the site investigator's report and determines causality of the adverse event. The MRO may request further information if necessary and possibly request changes to the protocol or

consent form as a consequence of the adverse event. A back-up notification system is in place so that any delays in review by the MRO beyond a specified period of time are forwarded to a secondary reviewer. Any follow up reports or requested additional participant data will be entered into the AEDAMS system by the reporting site and reviewed by the MRO. Completed AE reviews by the MRO will sent to Study Chair, site PIs, and the appointed NIH officers.

If warranted, the MRO may request an ad hoc call with the DSMB to review the adverse event. All reported AE's will be reviewed during the regularly scheduled DSMB call.

The Adverse Event Data Management System (AEDAMS) maintains audit trails and stores data (and data updated) and communication related to any adverse event in the study.

Non-serious expected adverse events: Except those listed above as immediately reportable, non-serious expected adverse events that are reported to or observed by the investigator or a member of his/her research team will be submitted to the DMCC in a timely fashion (within 20 working days). The events will be presented in tabular form and given to the MRO and RDCRN DSMB on a bi-annual basis. Local site investigators are also required to fulfill all reporting requirements of their local institutions.

The DMCC will post aggregate reports of all reported adverse events for site investigators and IRBs.

